Kits will be transported to RDB Bioinformatics laboratory for processing following sample acquisition. The dynamic surveillance software platform will guide proven, systematic phenotypic and genomic processing of collected samples in order to identify clonal transmission events occurring within and between operating room reservoirs in the observational unit (case pair). Guidance will be based on the strength of epidemiological-relatedness as follows: A transmission event will be defined as the presence of one or more isolates in a measured reservoir that was not present at case start. Transmission events within an observational unit will be further analyzed as directed by the RDB platform to identify clonally-related *S. aureus* transmission events.

The RDB Bioinformatics software platform will process transmission dynamics in order to continually summarize the epidemiology of *S. aureus* transmission. This information will be continually displayed in order to identify the most common reservoir of origin, the most common transmission locations (vectors), the most common mode of transmission (vertical or horizontal), and involvement of key portals of entry (stopcocks). To address strain characteristics, reports will focus on more pathogenic strains defined by the top 5 most transmissible, resistant, and virulent strain characteristics.

Automated analysis reports for overall transmission and for transmission of more pathogenic strains will be used by the infection control perioperative team to continually optimize the interventions affecting all patients in the treatment clusters as described further below. The platform will automatically quantify transmission events occurring in

treatment and control clusters such that involved in data collection and data entry will be blinded to the primary outcome.

All data will be analyzed by the statistician ([name]) at Dartmouth Hitchcock Medical Center who will not be involved in data collection.

Work flow: Monday-Friday only. Limited to patients that are seen in UIHC clinics. 1,000 case pairs: (500 treatment and 500 usual care) will be studied during the 2-year study period. This corresponds to one case pair in the “bundle” group and one case pair in the usual care group each day (5 days a week for 50 weeks each year). All patients will be followed for 90 days for infection development.

Data Handling: A multidisciplinary infection control perioperative team (the team comprised of surgical, nursing, anesthesia and infectious disease providers will manage the information provided by the S. aureus transmission surveillance instruments to proactively optimize the multimodal program outlined below.

Treatment Interventions: The following applies only to 500 patients in the “bundle” treatment group (500 patients will be sampled in the clinic and will receive the bundle. The case to follow the screened patient in the OR will be included in order to determine whether the optimized bundle for the first patient can prevent transmission of S. aureus to the second patient. The second patient will not receive the bundle. They will receive usual care. Both patients in the 500 treatment pairs (1000 total patients) will undergo surveillance). The 500 patients that are screened in the clinic in the control group will undergo usual care as will the patient to follow. Both patients in the 500 control pairs(1000 total patients) will undergo surveillance.

- Improved patient decolonization: The additional decolonization with povidone-iodine addresses antibiotic stewardship because S. aureus is becoming more resistant to topical antibiotics as a result of widespread use.
 - Improved vascular care and hand hygiene: All patients in the “bundle” treatment will receive closed, disinfectable stopcock sets (Ultraport Zero, BBraun Medical Inc, Bethlehem, PA 18018-3524), and catheter disinfection will be optimized with HubScrub and DOCit disinfection caps that address both the injection port and syringe tips (Saxa Medical Solutions, Mentor, OH 44060-4862) and leverage desiccation and mechanical disruption. Perioperative stopcock contamination rates will be monitored by surveillance reports filtered by stopcock involvement, and monthly reports of contamination will be used by the team to optimize catheter care via individual and group feedback. The vascular care system also contains a hand hygiene unit designed to link hand decontamination events with vascular care via proximity.
 - Improved environmental cleaning: Environments (OR and ward) affected by high-risk S. aureus transmission events will be mapped by surveillance and addressed by automated reporting to the anesthesia workroom supervisor. This will trigger improvements in routine (standard cleaning using quaternary ammonium compound and micro cloth followed by a surface disinfection wipe) and terminal [improved routine technique followed by employment of robotic cleaning (Ultraviolet light)] cleaning.
- Fatigue mitigation: The team will use surveillance to continually monitor the impact and fatigue of the proposed interventions as conveyed by failure mode analysis of transmission dynamics involved clonal S. aureus transmission.

XI.2

Provide the rationale or power analysis to support the number of subjects proposed to complete this study.

Statistical Analysis: The unadjusted primary intention to treat analysis will compare the proportion of clonally-related S. aureus transmission events occurring in treatment vs. control perioperative (preoperative, intraoperative case pair, and postoperative) observational units across the 6 randomized service lines using the Chi squared test. We will assess for balance for variables known to be associated with intraoperative

transmission (case, duration > 2 hours, and discharge location). In the case of imbalance, we will use multivariate techniques to further explore the treatment effect using a generalized linear models approach.

Initial Power Analysis (see amendment below based on reviewer concerns): We intend to screen a total of 1000 patients for up to 10 surgical service lines. Service lines will be randomized 1:1, yielding 500 patients in each treatment arm. Each patient will provide 4 observational units that include preoperative to intraoperative, intraoperative case 1 to intraoperative case 2, intraoperative case 1 to postoperative, and preoperative to postoperative opportunities for detection of *S. aureus* transmission. Thus, 500 patients in each arm will provide 2,000 observational units for a total of 4,000 observational units during the two-year study period. We originally calculated that this provided 90% power to detect a 30% relative reduction in the primary outcome (10.58% down to 7.41%). The estimated clonally related *S. aureus* transmission rate was based on a previously reported detection rate of 58 events in 548 observational units for all-comers to the operating room at 3 major academic medical centers in the United States. To address service line variation, we supposed that the logit-frequencies of the primary outcome for each service line were distributed as a normal distribution with a mean of -0.41 and standard deviation of 0.20. This amount of between-line variation corresponds to an intra-cluster correlation (ICC) of approximately 1%. It can also be interpreted as the amount of variation in which service lines in the top quartile of rates would have an average frequency (after removing within subsection binomial variation) of 46% while service lines in the lowest quartile have an average frequency of 33%. These calculations were accomplished using Monte Carlo simulations written in R 3.3, and using in part the following approximation for the ICC when rates are logit-normal, $1/(1+1/\sigma^2 \cdot \pi^2 \cdot \text{pa}(1-\text{pa}))$ (which can be readily derived using the delta theorem) where pa is the average frequency across centers and σ^2 is the standard deviation on the logit scale. We calculated that this provides 85% power to detect a 30% relative reduction in the primary outcome (40% down to 28%) if there is significant variation between service lines. If indeed there is no variation between service lines, the power is 98%.

We expect to lose some patients that are consented and enrolled in this study to non-compliance with study protocol. There may also be instances where the first OR case consented to the study but the following OR case does not consent on the day of surgery, making it an ineffective pairing for the study. Patients may also consent to the study when in the surgical clinic but change their mind and not consent to the study on the day of their operation. It is the patient's right to be able to exit the study at any time. In anticipation of patients who are consented but are not able to be used in the study we will need to consent more than the minimum 2000 total patients to reach the needed power. We estimate that consenting 2800 patients will give us enough room after drop-out/ineligibility due to a number of causes to generate a final amount of 2000 (as detailed above) successful patients that generate data for our study.

We have completed a pilot study at UIHC to evaluate the above power analyses. The pilot involved bacterial surveillance in approximately 40 observational units, or 80 cases. A total of 81 cases were enrolled because there was an unexpected cancellation. The primary outcome was intraoperative *S. aureus* transmission events. For the pilot, transmission events were defined as possible epidemiologically-related events, not yet clonal-additional testing required.

Below is a summary of the case-pairs observed stratified by service line.

Case Type # of Cases
Colorectal 10
Cardiothoracic 2
Gyn/onc 24

Orthopedics 44
Vascular 2
Total Cases 81

As orthopedic and gyn/onc procedures represented the majority of randomized units, we considered that those cases would serve as the best estimates for service line variation in *S. aureus* transmission detection. The incidence of *S. aureus* transmission detection ranged from 28% (orthopedic cases) to 58% (gyn/onc) cases. These results support our prior assumptions of anticipated service line variation, power calculations, and study design, and the variation is likely to be less with additional genomic analysis. Our hope is that this additional work and discussion can alleviate the reviewer concerns regarding study design.

XII. Future Research

- XII.1** *Do you wish to keep any information about subjects involved with this research project so that members of the current research team may contact them in the future for your own research projects?*
No
- XII.2** *Do you wish to keep any information about subjects involved with this research project so that [other researchers](#) may contact them for future research?*
No
- XII.4** *Does this project involve storing any data, tissues or specimens for future research?*
Yes – contribution for future use is mandatory for participation in the study

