Surgical service lines will include orthopedic total joint, orthopedic spine, gynecology/oncology, thoracic, general, hernia, colorectal, open vascular, plastic, and open urological procedures. These lines will be randomized 1:1 to either the bundle of activities or usual care. The unit of randomization is the service line. The perioperative environment (the patient, the patient to follow, and all providers caring for the patient and the patient to follow) for the randomized service line (treatment or usual care) will be involved in surveillance. This means that all patients, all providers caring for those patients (changes day by day), and care environments (equipment and stopcock sets) will be involved in surveillance. Surveillance from treatment and control groups will yield *S. aureus* transmission events that will be processed to guide proactive improvements in the treatment bundle.

Treatment group (bundle) inclusion/exclusion criteria:

Inclusion criteria: Patients seen at UIHC who are scheduled to undergo surgery from providers in one of the service lines above, documentation of informed, written consent, >18 years of age, procedure requiring general/regional anesthesia.

Exclusion criteria: Lack of documented informed, written consent, patients <18 years of age, procedures outside of the surgical service lines listed above, not requiring general/regional anesthesia, patients not seen in the UIHC clinics, and an allergy to iodine/shellfish or chlorhexidine.

Usual care group (existing practice at UIHC) inclusion/exclusion criteria:

Inclusion criteria: Patients seen at UIHC who are scheduled to undergo surgery from providers in one of the service lines above, documentation of informed, written consent, >18 years of age, procedure requiring general/regional anesthesia.

Exclusion criteria: Lack of documented informed, written consent, patients <18 years of age, procedures outside of the surgical service lines listed above, not requiring general/regional anesthesia, patients not seen at UIHC, and an allergy to iodine/shellfish or chlorhexidine.

VI.14

Provide an estimate of the total number of subjects that would be eligible for inclusion in each of your study populations (include your control population if applicable)

We anticipate that >80% of all patients undergoing surgery in the surgical service lines above will be eligible for the study.

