Reducing Perioperative S. aureus Transmission via use of an Evidence-Based, Multimodal Program Driven by an Innovative Software Platform (OR PathTrac)

9/20/2018

Statistical Analysis

Multiple statistical methods were used. For simplification, we list the statistical methods in the precise sequence they are reported in the results.

The Fisher exact test was used to compare patient and procedural demographic information for treatment vs control groups and for cases involving *S* aureus transmission. Similarly, the distribution of patients by ASA scores greater than 2 and by sex for enrolled vs eligible patients were compared by surgeon using the Mantel-Haenszel test.

The Fisher exact test was also used to examine the potential association of each of the covariates mentioned earlier with *S aureus* transmission. None were associated.

A 2-sided Wilcoxon-Mann-Whitney test was used to examine the association of treatment assignment with the number of transmitted *S aureus* isolates. Poisson regression was used to estimate the incidence risk ratio (IRR) of *S aureus* transmission for the independent variable of treatment. Poisson regression was used to estimate the IRR because the incidence of transmission was so large (ie, much greater than 10%) that the odds ratio estimated using logistic regression would be a biased estimator of the relative risk.²⁴ We repeated the analysis using multilevel Poisson regression clustering by surgeon or specialty.

The Fisher exact test was used to compare the proportion of patients in the treatment group with transmission events before vs after surveillance feedback and the proportion of patients with SSI with and without documented *S aureus* transmission. Poisson regression was used to compare the proportion of patients with SSI with and without documented *S aureus* transmission, clustered by surgeon.

The proportion of patients with SSIs was compared with the Fisher exact test. Time to infection was evaluated by Cox proportional hazard modeling. We repeated the analysis using multilevel Poisson regression clustering by surgeon and specialty.

There were no missing data for the primary and secondary outcomes. Calculations were performed using Stata version 16.1 (StataCorp). All P values were 2-sided, and P < .05 was taken to indicate statistical significance.

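### The primary chi-squared test ignores that service lines are randomised: on the protocol's own 40% assumption its false-positive rate is about 16% (10 lines) or 22% (6 lines), not 5%

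*Protocol*

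**What the plan says.** Protocol VI.13 states: "The unit of randomization is the service line". Lines are allocated 1:1 (VII.E.2), and XI.1 itself calls the arms clusters. XI.2 (Statistical Analysis) then gives as the primary intention-to-treat analysis an unadjusted comparison of transmission proportions in "observational units across the 6 randomized service lines using the Chi squared test". The only fallback is a generalised linear model, used if case, duration or discharge location is imbalanced. Service line is not named as a term in it.

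The power paragraph in XI.2 does allow for lines. It takes the line logit-frequencies as "distributed as a normal distribution with a mean of -0.41 and standard deviation of 0.20", equates this with an ICC of about 1%, and states 85% power for 40% against 28%. It adds: "If indeed there is no variation between service lines, the power is 98"%.

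Two design quantities are given in two ways:

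- **Lines.** The primary analysis says six. The power paragraph says "We intend to screen a total of 1000 patients for up to 10 surgical service lines", and VI.13 lists ten.
- **Unit.** XI.1 speaks of events "occurring within and between operating room reservoirs in the observational unit (case pair"), but XI.2 counts four units per patient: "Thus, 500 patients in each arm will provide 2,000 observational units for a total of 4,000 observational units".

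The SAP (Statistical Analysis) has no chi-squared test for transmission. Its treatment comparisons begin: "A 2-sided Wilcoxon-Mann-Whitney test was used to examine the association of treatment assignment with the number of transmitted" isolates. Single-level Poisson regression follows, and then a multilevel Poisson repeat with surgeon or specialty as the cluster. Significance is two-sided at 0.05. The SAP does not rank these results.

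**The concern.** A chi-squared test on units takes its standard error from binomial variation alone. When whole lines are allocated, the difference between arms also carries the difference between the few lines that fell in each arm. With three to five lines per arm, that difference does not average out. The protocol allows for it when it states power, but not when it tests.

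At stake is the primary claim: a chance difference between specialties could be reported as an effect of the bundle. The SAP adds a second problem. If its unclustered and clustered results disagree, no rule settles which one counts.

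**Working it through.** **Inputs.** Rates 40% and 28%, logit mean −0.41 and SD 0.20, and the 10.58% clonal rate (XI.2). 500 case pairs per arm (XI.1), or 2,000 units per arm (XI.2). 10 or 6 lines. Two-sided 0.05 (SAP). Equal line sizes are my assumption.

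**1. The plan's own power figures.**

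*No line variation, 500 per arm.* Pooled p = 0.34. The SE under the null is √(2 × 0.34 × 0.66/500) = 0.02996. The SE under the alternative is √((0.24 + 0.2016)/500) = 0.02972. Power = Φ((0.12 − 1.96 × 0.02996)/0.02972) = Φ(2.06) = 98.0%, as stated. So the stated figure rests on one result per case pair.

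*With line variation, 10 lines of 100.* The variance of a line proportion is (0.20·p(1−p))² + p(1−p)/100, which is 0.004704 at 40% and 0.003642 at 28%. With five lines per arm, SE = √((0.004704 + 0.003642)/5) = 0.0409. Power = Φ(0.12/0.0409 − 1.96) = 83.6%, or 85.7% if the relative risk is constant across lines. The stated 85% lies between. Six lines give only 72.7–76.0%. So the 85% needs ten lines and an analysis that carries the line variance. Under the same model with ten lines, the planned chi-squared test would reject in 93–94% of trials, so the 85% is not the power of the planned test.

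**2. Analytic false-positive rate of the chi-squared test, 40%, 500 per arm.**

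- ICC = 1/(1 + 1/(0.04 × 0.4 × 0.6)) = 0.0095, matching the stated 1%.
- Design effect = 1 + (m − 1) × ICC = 1.94 (10 lines of 100) or 2.58 (6 lines of 167).
- Type I error = 2(1 − Φ(1.96/√DE)) = 16.0% or 22.2%.

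**3. Simulation with no bundle effect, logit SD 0.20.** Entries are percentages, 10 lines / 6 lines.

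| Rate, units per arm | Chi-squared | Single-level Poisson | Multilevel Poisson by line, z | Same, t on lines − 2 df | Line-level t-test |
|---|---|---|---|---|---|
| 40%, 500 | 15.8 / 22.3 | 6.8 / 11.5 | 6.2 / 8.9 | 2.7 / 1.7 | 5.0 / 5.0 |
| 10.58%, 500 | 9.6 / 12.2 | 7.6 / 10.0 | 6.3 / 8.0 | 3.1 / 1.3 | 4.9 / 4.8 |
| 10.58%, 2,000 | 22.0 / 29.9 | 19.3 / 27.0 | 10.0 / 14.8 | 5.1 / 4.9 | 5.1 / 5.1 |
| 40%, 2,000 | 37.0 / 46.5 | 24.7 / 34.6 | 11.5 / 17.4 | 7.1 / 6.8 | 5.1 / 4.9 |

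The multilevel columns use 4,000–5,000 runs and the others 100,000. The multilevel columns take specialty to mean service line. Carrying SD 0.20 to the 10.58% rate is my extrapolation. The 2,000-unit rows leave out correlation among one patient's four units. The Poisson columns assume a yes/no outcome per unit and a Wald test. A separate run of 400,000 trials for the first row's chi-squared test gave 15.9 / 22.1, and 4.9 / 4.9 with SD set to zero, so line variation is the cause.

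**4. Sensitivity.**

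- *Chi-squared, 40%, 500 per arm:* SD 0.10 gives 7.7 / 9.7%. SD 0.30 gives 26 / 36%. Unequal lines (assumed 40:25:15:10:10 or 50:30:20 within each arm) give 18.9 / 24.1%.
- *Multilevel Poisson by surgeon* (assuming 3 to 8 per line, 2,000 runs): 6–7 / 9–12% with 500 per arm, and 16–26 / 22–35% with 2,000.
- *Wilcoxon:* not quantified, because no count distribution is given.

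**5. Power of the line-level t-test, 40% v 28%, 500 per arm.** 72.7 / 49.5% for a constant shift in log-odds, and 76 / 53% for a constant relative risk.

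**The case against.** The strongest reply is that the SAP does not use the chi-squared test for transmission and does fit a clustered model. Specialty is close to the randomised unit. With ten lines and one result per pair, that repeat runs at about 6%, close to nominal. This stands as credit to the SAP, but it does not close the point. The repeat drifts to 8–9% with six lines and to 10–17% with 2,000 units per arm. Surgeon lies below the randomised unit. Both documents carry the same date, and neither withdraws the chi-squared test that the protocol calls primary.

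Second, the 40% rate with 2,000 units per arm is the least supported row, because the 98% figure fits 500 per arm. Without it the chi-squared maximum is 29.9%, about six times nominal. That limits the top of the range, not the headline.

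Third, SD 0.20 is a supposition. XI.2 expects less variation after genomic analysis, while its pilot range (28% v 58%) points the other way. Neither was used here. Even at SD 0.10 the test exceeds its nominal level.

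Fourth, the single-level Poisson figures depend on the standard error. Model-based errors overstate the variance of a yes/no outcome (1.1% false positives with no line variation). With robust errors the 40%, 500-per-arm figures become 15.8 / 21.8%. The SAP states neither choice, so those figures are conditional.

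**Conclusion.** The concern holds. On the protocol's own 40% rate and SD 0.20, with equal lines and one result per case pair, the primary chi-squared test has a false-positive rate of about 16% (10 lines) or 22% (6 lines), three to four times the nominal 5%. Across the other readings of rate and unit the factor runs from about two to nine, with the top value resting on the least supported combination.

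The SAP's single-level comparisons share the fault. Its multilevel repeat reduces the error substantially, but it is neither corrected for 6 to 10 clusters nor given precedence. The SSI tests are outside this point. The primary efficacy claim rests on this choice, so it must be fixed.

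**What to change.** Make a service-line-level comparison the governing primary analysis: a t-test on line proportions or log-odds with lines minus 2 degrees of freedom. A model with a service-line random intercept and small-sample degrees of freedom is an alternative. In these settings it ran at 1.3–7.1% (1.3–3.1% with 500 per arm), so the t-test holds its level better.

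In the SAP, name service line as the cluster level, with surgeon nested if wanted. Specialty is not precise enough, since two of the ten listed lines are orthopaedic. State that this result governs, and report the chi-squared, Wilcoxon and single-level Poisson treatment comparisons as descriptive. Settle one number of randomised lines and one observational unit in both documents, because both set the error rate. Then restate the power for the test that will be used.

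No new data are needed. Intervals will widen, and power for 40% against 28% becomes about 73–76% (10 lines) or 50–53% (6 lines) instead of 85%. That loss comes from the few randomised lines, and reanalysis cannot recover it. The SAP is written in the past tense, so existing results may need to be reanalysed.

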The goal of the study is to reduce S. aureus transmission from known reservoirs during the perioperative period. One known reservoir is patient skin sites. That is why we are decolonizing patients before surgery. Another known reservoir is provider hands. That is why we are providing a hand hygiene system that is located close to the anesthesia provider so they can wash their hands at every opportunity. Conventional hand washing devices on the wall or on the anesthesia

machine do not facilitate hand washing during the fast-paced OR procedures. A third known reservoir is intravascular devices. That is why we are using the HubScrub and DOCit system that allows providers to scrub the hub at every opportunity with only 2 turns and within 10 seconds. A fourth known reservoir is the operating room environment itself. We are using surveillance to deploy strategic targeting of high risk environments as well as to continually optimize every component of the bundle over the 2 years. In summary, the study population is the perioperative period that includes patients, providers, equipment, environment, and even the air into which bacteria can be aerosolized for the patient and the patient to follow. The goal is to show that improved basic measures across the board in a dangerous environment like the OR can reduce high risk S. aureus transmission events.

Our primary outcome is S. aureus transmission events. The surveillance instrument as detailed in this proposal defines transmissions. Surveillance involves utilizing systematic reservoir collection kits (RDB Bioinformatics, Omaha, NE 68154) to collect S. aureus isolates from known reservoirs in perioperative environments. The OR PathTrac software (RDB Bioinformatics, Omaha, NE 68154) uses algorithms to guide analysis of the S. aureus isolates and to identify transmission events. Transmission stories are processed by the software to generate transmission maps that identify improvement successes and failures. It also identifies actionable steps to improve the bundle. The perioperative infection control team then uses this information to continually optimize the bundle, and the software to measure the effect.

The grant funding this research project will pay RDB Bioinformatics for the kits, for the analysis of the swabs for S. aureus, and for the OR PathTrac analysis on a fee-for-service basis. RDB Informatics is providing no funding for this study or in-kind support.

I.5

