We will also track patients who did not send the kits in (via EPIC reports). These patients will not undergo surveillance because they will not have

completed the required screening component. If three calls are made and they do not use the kits, they will be considered lost to f/u. This will be important information when results are reported.

VII.D.23 *Will this information be shared with anyone outside the UI research team members?*
No

VII.D.25 *After the subject agrees to participate (signs consent), are there any screening procedures, tests, or studies that need to be done to determine if the subject is eligible to continue participating?*
Yes

VII.D.26 *List and describe screening*
As described in VII.D.22, the patient must use and return the preoperative swab kits. Three reminders will be provided. If they do not complete the initial screening process, they will be considered lost to f/u. Information required to meet inclusion criteria will be self evident (age which is in the chart, surgical service line which is already known...they are in the randomized line, and need for general/regional anesthesia (this is decided by the procedure).

VII.D.27 *Discuss how much time a potential subject will have to agree to consider participation and whether or not they will be able to discuss the study with family/friends before deciding on participation.*
The patient will be seen in clinic, PAT, or on the floor/ICU as part of their visit. The initial time to decide will be limited by the study visit, as a preoperative order must be placed. However, they will be able to decline at any point down the road as previously described, including simply deciding not to use and return the ordered kit.

VII.D.28 *How long after the subject agrees to participate do study procedures begin?*
Our goal is to focus on a 10-day window prior to surgery so that the kit can be shipped (two days), received (two days), processed (up to 2 days), and in the treatment group, treated for 2-4 days.

VII.D.29 *Provide a description of the enrollment and consent process for adult subjects*

- *Describe each study population separately including control population*
- *Include when recruitment and consent materials are used*

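### The index patient's preoperative S. aureus swab, required in both arms, is not a named covariate in any analysis; adjusting for it would be a cheap but modest gain

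*Protocol*

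**What the plan says.** **The swab.** Protocol I.4 states "One known reservoir is patient skin sites" and gives this as the reason for decolonising patients. VII.D.26 makes the swab a condition of continuing: "the patient must use and return the preoperative swab kits". VII.D.29 sends a kit in both arms, with the kit type set by the service line. Carriage should therefore be on record for every surveilled index patient. Second patients of a pair get no preoperative kit (VII.E.6).

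**The protocol's analysis.** XI.2 reads: "The unadjusted primary intention to treat analysis will compare the proportion of clonally-related S. aureus transmission events", by chi-squared test. Balance is checked on variables linked to intraoperative "transmission (case, duration > 2 hours, and discharge location"). If they are unbalanced, "In the case of imbalance, we will use multivariate techniques to further explore the treatment effect using a generalized linear models approach". The confounder list in VII.E.6 contains medical-record items and no swab result.

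**The SAP's analysis.** Poisson regression estimates the risk ratio of "transmission for the independent variable of treatment". Then: "We repeated the analysis using multilevel Poisson regression clustering by surgeon or specialty". No baseline covariate is named in either model. Other covariates were screened one at a time with Fisher tests and reported as not associated, but the list itself is not in the text available.

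**The concern.** Carriage in the index patient is a plausible driver of S. aureus spread in that patient's operating room, and it is the reservoir that one bundle component targets. The mailed swab is the only candidate pre-treatment measure of it: the operating-room patient samples are taken after induction, and the Treatment Bundle text of VII.E.6 places povidone iodine on the day of surgery.

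The service line is the unit of randomisation, and XI.2 mentions 6 lines in one place and up to 10 in another. With so few units, a chance difference in carriage between arms is quite possible. An analysis that accounts for lines widens the interval but does not move the estimate back. A carriage difference could therefore make the bundle look somewhat better or worse than it is, and precision that is available at no extra data cost goes unused.

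**Working it through.** **1. The plan's own inputs.** XI.2 gives 500 index patients per arm, 40% reduced to 28%, and a between-line logit SD of 0.20. The stated 98% power without line variation reproduces (98.0%, two-sided 5%, normal approximation). The stated ICC of about 1% also reproduces: 1/(1 + 1/(0.20² × 0.4 × 0.6)) = 0.95%.

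**2. Assumed inputs, absent from the documents.** Carriage c = 30%; carrier risk ratio RR = 1.2, 1.5 or 2.0; SD of carriage between lines s = 5 to 10 percentage points; K = 6 or 10 lines. Overall risk p = 40% is from XI.2.

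**3. Formulas.**
- Risk in non-carriers: p/[(1 − c) + RR·c]. For RR 1.5 this is 0.40/1.15 = 34.8%, so carriers have 52.2% and the difference is d = 17.4 points.
- Shift in the arm difference per 10-point carriage difference: 0.10·d.
- Shift from a one-SD chance imbalance between lines: s·d·√(4/K).
- Outcome variance explained: R² = c(1 − c)d²/[p(1 − p)]. Equivalent gain in patients: 1/(1 − R²) − 1.

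| Carrier RR | 1.2 | 1.5 | 2.0 |
|---|---|---|---|
| d (points) | 7.5 | 17.4 | 30.8 |
| Shift per 10-point carriage difference (points) | 0.75 | 1.74 | 3.08 |
| One-SD shift, 6 lines (points) | 0.31–0.62 | 0.71–1.42 | 1.26–2.51 |
| One-SD shift, 10 lines (points) | 0.24–0.48 | 0.55–1.10 | 0.97–1.95 |
| R² | 0.5% | 2.65% | 8.3% |
| Equivalent gain in patients | 0.5% | 2.7% | 9.0% |
| Power gain, line-level t-test (points) | 0.1–0.2 | 1.0–3.5 | 3.2–11.7 |

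The last row is simulated (40,000 trials per cell, total line variation held at logit SD 0.20). A second run of 20,000 trials per cell gave gains of about 0, 0.7–2.7 and 3.3–11.2 points, with absolute power 2 to 4 points lower. The gains are more dependable than the levels.

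**4. Scale.** The SE of the arm difference is √[2 × ((0.20 × 0.24)²/(K/2) + 0.24/500)]. That is 5.0 points for 6 lines and 4.3 for 10. At RR 1.2 to 1.5, a one-SD shift is at most 1.42/5.0 = 0.28 SE.

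**5. The largest power gain.** The 11.7 points occur only with RR 2.0, s = 10 points and 6 lines. Carriage must then explain (0.10 × 0.3077/0.24)²/0.20² = 41% of the line variance. At RR 1.5 that share is 3–13%.

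**6. Lower baseline risk.** XI.2 also gives 10.58% for clonally related transmission. With p = 0.1058 in the same formulas, R² is 0.09%, 0.47% and 1.47%, so the gain falls to about 0.1%, 0.5% and 1.5%. At RR 1.0, every gain is zero.

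**7. Type I error.** In the simulation, chi-squared rejects a true null in 20–22% of trials with 6 lines and 14–16% with 10. Stratifying by carriage alone still leaves 11–22%. An unadjusted line-level t-test already holds 4.8–5.2%.

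**The case against.** **Chance imbalance is not an error in the plan.** A valid line-level interval already allows for it, so what is at stake is precision and the shift given the imbalance that occurs. This stands. A reader might infer that leaving carriage out invalidates the primary result or inflates type I error. Step 7 shows otherwise: the inflation comes from ignoring service lines, and a carriage term does not cure it.

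**Selection.** A reader might also infer that consent or kit return differs by carriage between arms, since kits are arm-specific and sent after lines are allocated. The documents do not support this. Inclusion criteria are near-identical (VI.13), VII.E.1.a says that some subjects are blinded, and nothing suggests that anyone knows carriage before the swab that measures it. It is a reason to report kit return, not a finding of bias.

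**The swab is partly built into the outcome.** It is the source sample for two of the four units per patient in XI.2 (preoperative to intraoperative, preoperative to postoperative). This stands and limits the remedy: for those units it should not be a covariate.

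**Carriage may predict little.** XI.1 counts isolates that were absent at case start, so a site that is already positive may not register an event. The pilot's 28% and 58% in two service lines show that lines differ, not that carriage is why. The effect of carriage may also differ by arm, because the bundle decolonises; a single carriage term averages over that.

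**Timing.** VII.D.28 and the opening of VII.E.6 can be read as decolonisation before the day of surgery, unlike the Treatment Bundle text. All three are compatible with a swab taken first, but none confirms it.

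**The SAP is in the past tense and reports results.** Its covariate list is not visible, so whether carriage was screened cannot be determined. A univariate screen would not in any case put it in the treatment-effect model.

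**Conclusion.** The omission is real: no analysis in the protocol or SAP names the preoperative swab result as a covariate, although the swab is mandatory for index patients in both arms and measures a reservoir that the bundle targets. The consequence is modest. A chance carriage difference stays in the estimate, and some precision is lost. At a carrier risk ratio of 1.2 to 1.5 the one-SD shift is about 0.2 to 1.4 points, against an SE of 4.3 to 5.0 and a planned difference of 12. Adjustment is worth roughly 0.5% to 9.0% more patients across risk ratios of 1.2 to 2.0 at 40% risk, less at 10.58%, and nothing if carriage does not predict the outcome. All of this rests on assumed carriage, risk ratio and line SD. It is a worthwhile low-cost improvement, not a flaw that undermines the trial.

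**What to change.** - In the treatment-effect model that accounts for service line, include index-patient preoperative carriage (yes/no) whatever the observed balance. Report the unadjusted result beside it.
- Use one yes/no outcome per case pair, the observational unit in VII.E.6 and XI.1, and reconcile this with the four units per patient in XI.2. Do not use the swab as a covariate for units in which it is the source sample.
- With so few lines, a two-stage form is workable: fit carriage only, then compare line residuals between arms by t-test on lines minus 2 df (4 df for 6 lines, 8 for 10). To keep the SAP's risk-ratio measure, use ratio residuals (observed over expected events per line). Otherwise, state that the result is a risk difference.
- Define carriage after reconciling the three swab sites in VII.E.6 with the nasopharynx alone in XI.1, and state that it describes the index patient only.
- Reconcile VII.D.28, the opening of VII.E.6 and the Treatment Bundle text so that the swab is confirmed as pre-treatment. If that cannot be confirmed, leave it out of the model.
- Report carriage and kit return by arm and line. VII.D.22 already provides for the latter: "We will also track patients who did not send the kits in (via EPIC reports").
- If outcomes were already known when this is added, label it a post hoc sensitivity analysis.

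The cost is one SAP paragraph, one extra parameter and a little analysis work, possibly for little gain. No new data are needed. The primary chi-squared test must still be corrected separately for randomisation by service line.
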